Not more than 20 ml of urine will be collected four times throughout the study. At Week 0 the urine will be used for the analysis of total nicotine equivalents (TNE) and other chemicals found in cigarettes. At Wks 12, 18 and 26 the urine samples will provide biochemical verification of cessation (via urine anabasine and anatabine, with the recommended cut-off of 2 ng/ml to

[figure not shown]
differentiate smokers from non-smokers). Not more than 20ml of saliva will be collected at Week 0 for genetic analysis. The DNA analysis will be used for research to understand nicotine metabolism genotype and phenotype. Melanin will be assessed at Wk 0 using a skin reflectometer.

Study Procedures:

Intervention

All eligible participants who provide written informed consent and complete the baseline survey will be randomized in a 1:1 fashion to either OPT or UC.

Optimization Overview. The optimization flow diagram is displayed in Figure 1. Both groups will receive 18 weeks of pharmacotherapy according to standard dosing guidelines^{6,49} but the type of pharmacotherapy will vary depending on group assignment and response. **Path A** is participants randomized to enhanced UC who will receive 18 weeks of NP (Wks 0-18). **Path B1** is OPT participants who respond to NP (CO LTE 5 ppm) at each optimization time point and, therefore, remain on NP for 18 weeks (Wks 0-18). **B2** is OPT participants who respond to NP at Wk 2 but who demonstrate non-response to NP at Wk 6 (CO GT 5 ppm) and are switched to VAR. Participants in this group will receive 6 weeks of NP (Wks 0-6) and 12 weeks of VAR (Wks 6-18). **B3** is OPT participants who were switched to VAR at Wk 2 after non-response to NP and who demonstrate response to VAR at Wk 6. Participants in this group will receive 2 weeks of NP (Wks 0-2) and 16 weeks of VAR (Wks 2-18). **B4** is OPT participants who were switched to VAR at Wk 2 and BUP +NP at Wk 6. Participants in this group will receive 2 weeks of NP (Wks 0-2), 4 weeks of VAR (Wks 2-6), and 12 weeks of BUP +NP (Wks 6-18).

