Final Screening and Enrollment (Wk 0). Final eligibility screening will be conducted in person and will consist of a pregnancy test on women of childbearing age and obtaining informed consent.

Counseling Visits (Wks 0, 1, 2, 3, 6, 7, 12). Counseling sessions, each lasting approximately 20 minutes, will be completed in person at Wks 0, 2, 6, 12 and by telephone at Wks 1, 3, 7. The number of sessions is consistent with our previous studies where we have achieved visit completion rates of ~ 80%.^{12,14,15,19}

Response/Non-Response to Pharmacotherapy (Wk 2, 6). Exhaled air carbon monoxide

(CO) is an immediate, non-invasive method of biochemically verifying smoking status. At Wk 2 and 6, all participants will breathe into a Micro-3 Smokerlyzer (Bedfont Scientific) for the purpose of determining abstinence. All participants will be informed of their CO level and it will be used to frame counseling discussions around smoking status/quitting. OPT participants with CO LTE 5 ppm will be considered 'responders' and will continue on their existing pharmacotherapy. Those with CO GT 5 ppm will be considered 'non-responders' and will be switched to the next pharmacotherapy per Figure 1.

Medication Dispensing (Wk 0, 2, 6, 12).

Medication will be dispensed at Wk 0 (baseline) and Wk 2, 6, 12 in the quantity needed to get participants to the next assessment/optimization time

point. This approach has resulted in 88% attendance at medication dispensing visits in our previous studies. Participants will be asked to return unused medication to ensure (a) that OPT participants take only the medication corresponding with the current stage of treatment and (b) that OPT and UC participants on NP receive a supply that corresponds with their current dosing needs. Those who do not attend medication dispensing visits will be mailed enough of their *current* medication to get them to the next dispensing time point. Participants must be eligible for NP, BUP, and VAR as a condition of eligibility; however, prior to switching, we will reassess medical eligibility in OPT non-responders. Given the short time frame between visits and careful upfront screening, we expect that very few non-responders will be medically ineligible for switching. Those who are will either receive the next therapy for which they are eligible (BUP, VAR) or, if medically ineligible for either switch, stay on their existing pharmacotherapy.

COVID-19 Remote Visits.

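### A participant found medically ineligible at the pre-switch check could, on the written rules, be kept on the current drug, and no eligibility check is written for the 12 to 16 weeks after a switch

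*Combined protocol and SAP*

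**What the plan says.** Section II.D excludes people who are pregnant, planning pregnancy or breastfeeding, and people with medical contraindications to any of the three drugs. Under Final Screening and Enrollment (Wk 0) in Section II.E, "Final eligibility screening will be conducted in person and will consist of a pregnancy test on women of childbearing age".

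Under Medication Dispensing in Section II.E:

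- The later check: "prior to switching, we will reassess medical eligibility in OPT non-responders". What it covers is not itemised.
- The reason given for expecting little trouble: "Given the short time frame between visits and careful upfront screening, we expect that very few non-responders will be medically ineligible for switching".
- The fallback: such participants get whichever of bupropion or varenicline they can take or, "if medically ineligible for either switch, stay on their existing pharmacotherapy".
- Missed visits: "Those who do not attend medication dispensing visits will be mailed enough of their" current drug to last until the next dispensing point.

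The Optimization Overview gives the time on drug. For path B3: "Participants in this group will receive 2 weeks of NP (Wks 0-2) and 16 weeks of VAR (Wks 2-18". B2 has varenicline from week 6 to week 18. B4 has varenicline from week 2 to week 6 and then bupropion plus patch to week 18.

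The medication supervision text, before the drug-by-drug descriptions in Section II.E, provides for stopping or reducing drug after a serious adverse event, or after other adverse events that the clinical team considers to warrant it. It also prompts participants about side effects at in-person visits, gives them a telephone number, and refers problems needing medical attention to a study physician. The discussion of approved medications and the adverse event text, both late in Section II, add physician supervision and adverse event tracking.

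**The concern.** There are two linked gaps.

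The first is an instruction. The fallback asks whether a participant can take the next drug. It does not ask whether the finding that rules out the next drug also rules out the current one. Where it does, the written rule is to carry on, and the stop rule does not catch the case, because a pregnancy or a newly started contraindicated medicine need not present as an adverse event.

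The second is an omission in the available text. Eligibility is checked at entry and again before a switch, but not afterwards. The adverse event text late in Section II names the exclusion criteria and adverse event monitoring as the means of protecting participants. Several of those criteria, pregnancy among them, can change during 18 weeks of treatment. The protocol's appeal to short intervals between visits fits the period before a switch, not the longer period after it.

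At stake is the safety of a probably small number of OPT participants.

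**Working it through.** **Inputs.** Switch decisions at weeks 2 and 6, and dispensing at weeks 0, 2, 6 and 12 (Section II.E). Treatment ends at week 18 (Optimization Overview). OPT has 196 participants (Section II.B). Attendance at dispensing visits was 88% in the team's previous studies (Medication Dispensing).

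**Time on drug after the last written check** = 18 minus the week of that check.

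| Path | Last check | Drug afterwards | Weeks |
|---|---|---|---|
| B2 | Wk 6 | varenicline | 18 − 6 = 12 |
| B3 | Wk 2 | varenicline | 18 − 2 = 16 |
| B4 | Wk 6 | bupropion + patch | 18 − 6 = 12 |

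These reproduce the protocol's own durations of 12, 16 and 12 weeks. B4's first segment, 6 − 2 = 4 weeks of varenicline, is followed by a check at week 6. B3 participants respond at week 6, continue unchanged, and so meet no second check. The week 12 dispensing covers 18 − 12 = 6 more weeks without one.

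**The fallback and the stop rule side by side.** At week 2 the existing drug is always the patch, so the fallback can hold someone only on the patch. At week 6 a participant who switched at week 2 is on varenicline. Suppose that participant has CO above 5 ppm and the pre-switch check finds a pregnancy.

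1. Pregnancy is an entry exclusion for the whole trial, so bupropion plus patch is not open.
2. The fallback then leaves the participant on varenicline.
3. The stop rule needs an adverse event, and none has occurred.
4. Followed literally, varenicline continues to week 18, a further 18 − 6 = 12 weeks.

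**Effect of asking at weeks 6 and 12.** The longest stretch without the questions becomes max(6 − 2, 12 − 6, 18 − 12) = 6 weeks, against 16 now, for participants who are reached. This counts question sets, not laboratory tests.

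**Workload.** Beyond the pre-switch checks already planned, B2 and B4 need one extra set (week 12) and B3 needs two (weeks 6 and 12). The ceiling, if all of OPT followed B3, is 2 × 196 = 392 sets. At 88% attendance, 100% − 88% = 12% miss a given dispensing visit, and 0.12 × 196 = 23.5, so at most about 24 OPT participants per visit would need a separate call.

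**The case against.** The strongest reply is that the text is incomplete. A stretch of Section II shortly before the drug-safety text, and the consent pages, are not in the copy reviewed, and the pre-switch check may well cover pregnancy. A reader might infer that pregnancy is never tested again after week 0. The documents do not support that. They describe no later test, which is weaker, and the point does not rest on it. The wording of the fallback and the stop rule can be read directly.

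Second, the fallback can be read as an allocation rule, silent on safety. For a varenicline non-responder who simply cannot take bupropion, staying on varenicline is a sensible default. That stands, and it is why the sentence needs a condition and not removal.

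Third, a reader might infer that the protocol has no way to stop drug, or that staff would knowingly treat a pregnant participant. Neither follows. There is a stop rule for adverse events. The discussion of approved medications describes ending varenicline when it is not working. Study physicians supervise treatment, and the referral of medical problems to them is not confined to adverse events. They would probably stop the drug whatever the fallback says. But none of this text names pregnancy or a new contraindication as a reason to stop.

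Fourth, Section II.D refers to contraindicated medications without listing any, so the documents do not show how often a new one could arise on varenicline. This also stands, and it limits the size of the point.

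**Conclusion.** The point holds as a minor one, with two parts. The written fallback, combined with a stop rule limited to adverse events, points the wrong way for a participant whose ineligibility extends to the current drug; for varenicline this arises at week 6. And no eligibility check is written for the 12 weeks (B2, B4) or 16 weeks (B3) on varenicline or bupropion plus patch after the last switch.

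It rests on three assumptions: that the missing text adds no such check or stop rule, that the named paths are followed as described, and that pregnancy or a contraindication serious enough to bar entry is also a reason to reconsider continuing. Only OPT participants receive these drugs, so at most 196 of 392 are exposed. The documents give no rate for pregnancy or new contraindications, so the number affected cannot be calculated.

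The length of the unchecked period is not a measure of risk: participants are still seen in person and asked about side effects during it. Nor should a reader infer an effect on the comparison of arms. No effect on bias, the week 12 endpoint or power is claimed.

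**What to change.** 1. **Fallback (Medication Dispensing).** Allow a participant who cannot switch to continue the existing drug only while still medically eligible for it; otherwise stop study drug.
2. **Stop rule (medication supervision text).** Add pregnancy and a new contraindication to the current drug as triggers. State that anyone who stops drug remains in follow-up at weeks 12, 18 and 26.
3. **Checks at weeks 6 and 12.** At the dispensing contact, in person or by telephone, ask participants on varenicline or bupropion plus patch the existing screening questions on pregnancy, new medications and new contraindications. Refer any positive answer to the study physician before drug is released.

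The cost is two edited sentences, a few minutes per contact, and an extra call for those who miss a dispensing visit (at most about 24 of 196 per visit). If someone cannot be reached through the existing reminder calls, mail the supply as now and flag the participant to the study physician. That avoids delaying OPT supply relative to UC before the week 12 endpoint, at the price of leaving those participants unchecked until the next contact. The questions would not detect a pregnancy that the participant does not know about.

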The current study involves three FDA-approved smoking cessation medications -- nicotine patch (NP), bupropion (BUP), and varenicline (VAR). These medications do not require an investigational new drug application and are being used in accordance with cleared/approved labeling. Specifically, nicotine patch is available over-the-counter without a prescription and is approved for long-term use.

Participants in the current study will use the nicotine patch for up to 18 weeks or for a shorter duration if it is determined that the nicotine patch is not working for them. Bupropion (BUP) and varenicline (VAR) both require a prescription. Participants will receive clearance from a physician to use these products before being enrolled and will be under the medical supervision of a physician during the course of the study. Treatment with VAR has been approved for up to 24 weeks, with the standard course of treatment being 12 weeks.⁵⁰ Participants in the current study will receive VAR for 4 weeks, 12 weeks, or 16 weeks. The shorter course of treatment (i.e., 4 weeks) will only occur if VAR is not working for the participant (i.e., they are not quit and/or are experiencing substantial nicotine-related withdrawal or craving and medication-related adverse events). These are standard instances in which the use of VAR would be terminated. Treatment with BUP has been approved for up to 12 months, with the standard course of treatment lasting from 6 – 12 weeks.⁵⁰ Participants in the current study will use BUP

for 12 weeks. The black box warning for both BUP and VAR has been removed (<https://www.fda.gov/Drugs/DrugSafety/ucm532221.htm>) due to evidence that these medications do not increase neuropsychiatric harm relative to placebo; this is true in individuals with and without a mental health diagnosis.⁵⁴

This study does not involve more than minimal risk. We will protect participants and minimize risks by using the strict exclusion criteria and careful monitoring of adverse events (AEs). AEs will be tracked during regularly scheduled provider visits or through spontaneous reports made by participants. Drs. [name], [name] (or the treating provider) and [name] will be made aware of unexpected or serious AEs within 24 hours of the first report by participants; all other AEs will be reviewed weekly by [name] and discussed at regular meetings with [name]. SAEs will be reported to the KUMC IRB, FDA, and NIDA within 24 hours of first awareness of the event. Unexpected adverse events that are related to the study medication will be reported to KUMC IRB, FDA, and NIDA within 5 working days of first awareness of the event if the event is not serious fatal and within 24 hours of first awareness if the event is serious. Unexpected adverse events that are unrelated to the study medication will be reported to the KUMC HSC during yearly routine event reporting. IRB actions taken in this study will be reported to NIDA. Drs. [name] or [name] (or the treating provider) will determine relatedness for each reported AE. SAEs will be defined as any event experienced by a study subject while on the study medication that is fatal, life-threatening (subject was at risk of death from the event as it occurred), disabling or incapacitating, requires inpatient hospitalization or prolongs a current hospitalization, is a congenital anomaly in the offspring of a subject who received the study medication, or required intervention to prevent permanent impairment or damage.

III. Subject Participation

A. Recruitment:

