The above studies support the strong scientific premise for an optimized approach to tobacco dependence treatment. Notably, 70-91% of participants in the above studies have been White smokers.³⁹⁻⁴³ AAs have different smoking patterns and behaviors, including a preference for

menthol cigarettes, fewer CPD, and different preferences for and responses to pharmacotherapy, including differences in nicotine and pharmacotherapy metabolisms.^{12,15,19,46-48} Therefore, the selection and sequence of smoking cessation medications

II. Research Plan and Design

A. Study Objectives

The objective of this study is to examine the efficacy of optimized (OPT) versus enhanced usual care (UC) treatment for smoking cessation. AA smokers randomized to OPT (n=196) will receive high intensity smoking cessation counseling, nicotine patch (NP), and up to two pharmacotherapy optimizations [bupropion (BUP), varenicline (VAR)] based on verified smoking status at Weeks 2 and 6. AA smokers randomized to enhanced UC (n=196) will receive the same high intensity counseling and NP with no optimizations in pharmacotherapy.

B. Study Type and Design

The proposed study is a randomized adaptive treatment trial for smoking cessation in 392 AA smokers. Participants randomized to OPT (n=196) will receive smoking cessation counseling, nicotine patch and up to two pharmacotherapy adaptations (VAR, BUP+NP) based on verified smoking status at Weeks 2 and 6. Participants randomized to UC (n=196) will receive the same smoking cessation counseling and NP; pharmacotherapy in this group will not be optimized. Pharmacotherapy and counseling in both groups will last for 18 weeks with long-term follow-up through Week 26. The primary outcome is biochemically-verified smoking status at Week 12.

C. Sample size, statistical methods, and power calculation

392 eligible AA smokers will be randomized. We will use a 1:1 fashion to either OPT or enhanced UC. Randomization will be stratified based on to ensure an equal proportion of male and female smokers in OPT and UC. Randomization will be determined by computer-generated random numbers. Randomization assignments will be placed in sealed envelopes with sequential study ID numbers. After baseline data collection has been completed, the research assistant will select the sequential study ID number to determine the randomization assignment.

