Use of study medication will be under the supervision of Drs. [name] (PI), [name] (Co-I and Kansas study physician), and [name] (Co-I and Missouri study physician). Participants will be prompted to discuss side effects at each in-person visit and given the study phone number to report adverse events at interim time points. NIH guidelines for reporting serious adverse events (SAEs) will be followed. Any problems needing medical attention will be referred to Drs. [name] or [name] who will carry a study pager and have served in this role in previous RCTs. Medication will be discontinued or reduced following a SAE or in the event of AEs judged by the clinical team to warrant discontinuation or reduction. In our previous RCTs with these medications only 3% of participants required discontinuation and 1% required reduction.

NP (OPT, UC). To maximize efficacy, all participants will receive the 24-hour 21 mg NP for 18 weeks. NP therapy will start at Week 0, with the 1st TQD occurring at Week 1.

VAR (OPT). VAR will be dispensed 0.5 mg once daily on Days 1-3, 0.5 mg twice daily on Days 4-7, and 1 mg twice daily from Day 8 through the EOT. The new (2nd TQD will be Day 8 of VAR. Treatment with VAR has been approved for up to 26 weeks, with the standard course of treatment being 12 weeks.⁵⁰ Non-responders in the current study will receive VAR for 4 weeks (Path B4), 12 weeks (B2), or 16 weeks (B3).

BUP (OPT). BUP will be dispensed 150 mg once daily on Days 0-3 and then 150 mg twice daily from Day 4 through optimization or the EOT. The new (3rd) TQD will be Day 8 of BUP. Treatment with BUP has been approved for up to 12 months, with the standard course of treatment being 12 weeks.⁵⁰ Non-responders in the current study will use BUP +NP for 12 weeks (Path B4).

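### The SAE definition stops when study medication stops, so some serious events after early discontinuation or in Weeks 18-26 have no prompt external reporting route

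*Combined protocol and SAP*

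**What the plan says.** The adverse-event monitoring paragraph, just before III. Subject Participation, sets the definition: "SAEs will be defined as any event experienced by a study subject while on the study medication that is fatal". Life-threatening events, disability, hospitalization, congenital anomaly and events needing intervention to prevent permanent damage follow in the same sentence.

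The same paragraph gives three external reporting rules:

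- For SAEs: "SAEs will be reported to the KUMC IRB, FDA, and NIDA within 24 hours of first awareness of the event".
- For unexpected events related to study medication: five working days to the same three bodies, shortened to "within 24 hours of first awareness if the event is serious".
- For the rest of the unexpected events: "Unexpected adverse events that are unrelated to the study medication will be reported to the KUMC HSC during yearly routine event reporting".

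It also has the study clinicians told of unexpected or serious events within 24 hours of the participant's report.

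II.B gives the time frame: "Pharmacotherapy and counseling in both groups will last for 18 weeks with long-term follow-up through Week 26". II.E (Intervention) foresees early stopping: "Medication will be discontinued or reduced following a SAE or in the event of AEs judged by the clinical team". The same part of II.E says NIH guidelines for SAE reporting will be followed, without stating a collection window. It also says participants are asked about side effects at every in-person visit.

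**The concern.** Whether an event is serious should depend on what happened to the participant. Here it also depends on whether the participant was taking study drug at the time. There is no post-dose window, not even one day, and no reason is given. A participant who stops a drug because of an adverse event and is hospitalized a few days later has, on the wording, no SAE. The same is true of anyone hospitalized in Weeks 18-26, although the trial is still following them.

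What is at stake is safety oversight. The 24-hour report to the IRB, FDA and NIDA is triggered by the SAE definition, and internal notice to the study clinicians does not replace it. The efficacy conclusion is not affected.

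**Working it through.** **1. Treatment length.** Inputs are the path durations in II.E (Optimization Overview).

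| Path | Weeks on drug |
|---|---|
| A (UC) | 18 |
| B1 | 18 |
| B2 | 6 + 12 = 18 |
| B3 | 2 + 16 = 18 |
| B4 | 2 + 4 + 12 = 18 |

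This reproduces the plan's 18 weeks in both groups. It also shows that scheduled switches are back to back. For B4 the text reads "2 weeks of NP (Wks 0-2), 4 weeks of VAR (Wks 2-6), and 12 weeks of BUP +NP (Wks 6-18".

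**2. Planned follow-up outside the definition.** Follow-up ends at Week 26 (II.B).

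- Per participant: (26 - 18) / 26 = 8 / 26 = 30.8%.
- All 392 participants at full retention: 392 × 8 = 3,136 of 392 × 26 = 10,192 person-weeks.

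**3. Adding early stoppers.** II.E reports that 3% of participants needed discontinuation in the team's earlier trials.

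- 0.03 × 392 = 11.76, about 12 people.
- Assume they stop on average at Week 9, the midpoint of treatment. Extra off-drug time is 11.76 × 9 = 105.84 person-weeks.
- Share outside the definition: (3,136 + 105.84) / 10,192 = 31.8%.

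Early stoppers add little time. They matter because the plan itself expects some participants to stop for safety reasons.

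**4. Routes for an off-drug serious event.** Setting the three rules against each type of event:

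| Off-drug serious event | SAE 24-hour rule | Other stated external route |
|---|---|---|
| Unexpected, related | Does not apply | 24 hours if *serious* has its ordinary meaning; if it imports the on-drug definition, apparently five working days |
| Unexpected, unrelated | Does not apply | Yearly, to the KUMC HSC only |
| Expected, related | Does not apply | None stated |
| Expected, unrelated | Does not apply | None stated |

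On drug, all four types would be SAEs and would go out within 24 hours.

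**5. How many events.** The documents give no SAE rate, so the following is an assumption shown over a range. Let r be the 26-week SAE risk per participant, with constant hazard h = -ln(1 - r) / 26. Expected events in Weeks 18-26, both arms together and at full retention, are 392 × 8 × h.

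| Assumed r | Expected events, Weeks 18-26 |
|---|---|
| 1% | 1.2 |
| 2% | 2.4 |
| 3% | 3.7 |
| 5% | 6.2 |

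Only some of these would lack a 24-hour route, depending on how they divide among the four rows in step 4.

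**The case against.** The strongest reply is that the same paragraph already covers the events of most concern. Unexpected, drug-related events that are serious go to the IRB, FDA and NIDA within 24 hours, and that sentence does not repeat the on-drug condition. Clinicians also hear of serious events within 24 hours, NIH guidelines are invoked, and side-effect questions at in-person visits are not confined to time on drug. The drugs are approved products that the plan says are used within labeling, so an on-treatment window could be called a design choice.

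Much of this stands. A reader might infer that drug-related events after stopping would go unreported. The documents do not support that, because the second 24-hour route may well catch the unexpected ones. But the only definition of seriousness in the available text is the on-drug one, so the route is ambiguous. On any reading it leaves out expected events and unrelated ones. Clinician notice is internal. The NIH reference has no stated window and sits beside an explicit, narrower definition.

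Four other stronger readings should not be drawn:

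- **Events between two drugs are lost by design.** The switch paths are contiguous. Only an unplanned gap, such as not restarting after a switch, could matter.
- **The between-arm safety comparison is distorted.** None is planned in the available text. V.A and V.B point to II.C, which covers abstinence only, and both arms have the same planned 18 weeks of drug.
- **The congenital-anomaly criterion can never be met.** It reads "is a congenital anomaly in the offspring of a subject who received the study medication". Men are enrolled, and a male participant's child could be born during his treatment.
- **About 80% visit completion means many participants are off drug.** II.E says those who miss a dispensing visit are mailed their current medication.

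**Conclusion.** The point holds in a limited form. As worded, the definition puts serious events after early discontinuation, and all serious events in Weeks 18-26, outside the SAE 24-hour rule. That is 8 of 26 planned weeks (31%), or about 32% under the 3% discontinuation figure and the assumed Week 9 average stopping time. These are shares of time, not of events.

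The clear gaps are expected off-drug serious events, which have no stated external route, and unexpected unrelated ones, which are reported only yearly. For unexpected related events the text is ambiguous.

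The number of events affected cannot be known from the documents and is probably small. An assumed 26-week risk of 1% to 5% puts about 1 to 6 events in Weeks 18-26 across both arms, and only a subset would lack prompt reporting. The conclusion rests on a literal reading of the definition and on the available text, in which no other SAE window appears.

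**What to change.** In the adverse-event monitoring paragraph, define an SAE by the seriousness criteria alone, for any event from first dose through the Week 26 visit, whether or not study medication is being taken. State that this definition governs both 24-hour rules, so that *serious* means the same in each. Reconcile it with the NIH guideline reference in II.E (Intervention), so that the plan has one definition and one explicit start and end for SAE collection.

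The cost is a short amendment and a few more SAE reports. No new visits are needed, because the Week 18 and Week 26 assessments already exist. Sample size and the primary analysis do not change.
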